1.2.2 Power Analysis

Consistent with the intervention development goals of Phase 2, we are not powered to detect significant between-condition differences in primary outcomes for that phase. Power analyses for Phase 3 were conducted based on our preliminary pilot data extracted from a similar study (R34 DA036419; PI [name]) testing adjunct CHTC components in emerging adult gay male couples aged 18-29 years. Preliminary results from the 3 month wave of data collection (the most distal available with sufficient data to estimate effects at the time of protocol paper submission) suggested that viewing ACT videos prior to CHTC was associated with a 56% decrease in the odds of CAS with a casual partner (relative to CHTC alone) among HIV negative participants not on PrEP. Of particular relevance to our mediation hypotheses, viewing ACT videos prior to CHTC was associated with a 5 to 6 point decrease in avoidant communication as measured by the Communication Patterns Questionnaire (CPQ) [54]. In turn, CPQ avoidant communication scores had a significant positive association with CAS with casual partners among HIV negative men not on PrEP ($\exp B = 1.06, p < .01$). Separately, our previous study of brief MI interventions with YMSM suggest it is associated with as much as an 83% reduction in the odds of CAS with a casual partner [55] compared to an attention-matched psychoeducation control condition.

These preliminary effect sizes were utilized as parameters in power analyses using a Monte Carlo simulation approach in Mplus (version 7.3)[53]. This approach provides a direct estimation of power while modeling both the multilevel structure of data (individuals are nested within couples) and the longitudinal design of the study (each individual provides data at 3 follow-up points). The program generates random samples from the specified population and, within each sample, examines the significance of freed parameters. Power is defined as the proportion of simulated samples in which the freed parameter has a p value of less than .05. All models specified a random seed and used 10,000 sample replications. Power analyses conducted based on these preliminary effect sizes suggests that $n = 144$ couples ($n = 288$ individuals), anticipating a minimum of $n = 232$ individuals retained at 6 months, is adequate to achieve power $> .80$ for all hypothesized direct effects as well as indirect pathways.

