2.0 Objectives*

Aims: We will conduct a comparative effectiveness trial (CET) of Couples HIV Testing and Counseling (CHTC) for adolescent-age (15-24 years) same-sex male couples. This design tests the added benefits of adjunct intervention components delivered prior to receipt of CHTC-Assertive Communication Training (ACT) videos viewed by the couple separately and individually delivered Motivational Interviewing-based Communication Skills Training (MI-CST). These target the development of communication skills necessary to participate fully in HIV prevention and sexual safety discussions inherent to CHTC. This project will assess a continuum of intervention packages to address the developmental needs of YMSM (CHTC; ACT videos + CHTC; MI-CST + ACT videos + CHTC) to identify which package optimizes outcomes while minimizing delivery cost.

Aim 1: Conduct a sequence of randomized control trials (RCTs) to evaluate the acceptability, feasibility, and comparative effectiveness of novel treatment packages.

Aim 1a: In study Phase 2, we will conduct a pilot RCT to evaluate the acceptability and feasibility of adjunct intervention components. This initial trial will recruit n=36 couples who will be randomized to one of 3 conditions: Condition 1: CHTC (only); Condition 2: couples' joint observation of ACT videos + CHTC; Condition 3: each individual within couple receiving MI-CST + joint observation of ACT videos + CHTC. Youth will then complete follow-up assessments at 1 and 3 months post-intervention. YOUTH DO HAVE THE OPTION OF COMPLETING THE INTERVENTION ON THEIR OWN IF THEY CAN NOT GET THEIR PARTNER TO AGREE TO PARTICIPATE. During Phase 3, we will recruit 200 individuals into a CET with two conditions: Condition 1: the optimum adjunct intervention package identified in Phase 2 and Condition 2: Individual HIV Testing (IHTC) as usual. Youth in this CET will complete follow-up assessments at 1, 3, and 6 months. Youth have the choice of attending the baseline visit alone or with their partner and have the option to bring their partner in later after completing the baseline alone.

Aim 1b: Assess self-management model; we posit that assertive communication skills will mediate intervention effects at all follow-ups. In study Phases 2 and 3, we anticipate between-condition differences will be greatest among YMSM with poor baseline assertive communication.

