Aim 2: Test a sustainable model of CHTC implementation in real world adolescent HIV clinics. In line with the implementation science focus of SIU U19, we utilize the EPIS to guide our implementation strategy. We will work with SIU Analytic Core's (AC) health-economist, [name], to conduct cost-effectiveness analyses to inform implementation decision-making. In collaboration with SIU ISC, we will document provider feedback to training and intervention materials to modify materials and create training packages for broad dissemination.

We will achieve our aims over two phases of the study.

PROTOCOL TITLE:

Phase 2 (n=36 couples): involves a pilot randomized control trial (RCT) to evaluate the acceptability, feasibility, and preliminary efficacy of these adjunct components.

Phase 3 (n=200 individuals): involves a CET comparing the most promising intervention package from Phase 2, consisting of individual MI, ACT video+ a recognition survey, and CHTC, compared to individual HIV testing and counseling (IHTC) delivered as usual. Participants in either condition can come as an individual or with their partner or come first as an individual and then bring their partner. This phase is focused on Implementation and Sustainment phases of the EPIS model informed by outcome analyses, cost analyses, and feedback from youth and ATN staff.

Phase 3 has now been added to this protocol document.

Hypothesis: The primary hypothesis is that because of developing skills in self-management and assertive communication, inclusion of adjunct components will be associated with clinically significant decreases in HIV transmission risk behavior as compared with partnered YMSM who receive individual testing and counseling (only). Secondarily, we propose that these intervention effects will be mediated by assertive communication skills.

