1.2 Quantitative Analysis Plan

The primary hypothesis is that due to developing skills in self-management and assertive communication, inclusion of adjunct components will be associated with clinically significant decreases in HIV transmission risk behavior (TRB) as compared to partnered YMSM who receive CHTC (only). Secondarily, we propose that these intervention effects will be mediated by assertive communication skills. As stated above, we focus on four behavioral indicators of TRB. At the individual-level, we examine: (1) number of CAS acts with a casual partner in the absence of PrEP and (2) any positive chlamydia or gonorrhea diagnoses in the absence of PrEP. At the couple-level, we will examine (3) any sex in the absence of PrEP with a primary partner who reports CAS with a casual partner; and (4) any sex in the absence of PrEP with a primary partner who receives a positive chlamydia or gonorrhea diagnosis. Any missing data and additional covariates will be informed by attrition analyses prior to primary analyses.

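### The Phase 3 power claim (> .80) is for 144 couples (288 individuals) and effect sizes not measured against IHTC; the protocol plans 200 individuals, allows solo enrolment and compares with IHTC

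*SAP*

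**What the plan says.** The SAP's Power Analysis section applies to Phase 3. It states that the simulation "suggests that $n = 144$ couples ($n = 288$ individuals), anticipating a minimum of $n = 232$ individuals retained at 6 months" and that this "is adequate to achieve power $> .80$ for all hypothesized direct effects as well as indirect pathways". Two effect sizes feed it:

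- For ACT videos before CHTC, a "56% decrease in the odds of CAS with a casual partner (relative to CHTC alone", among HIV-negative participants not on PrEP.
- For brief MI, a reduction in the same odds of up to 83%, "compared to an attention-matched psychoeducation control condition".

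The simulated data have individuals nested in couples and three follow-up points. SAP 1.2 frames the primary hypothesis "as compared to partnered YMSM who receive CHTC (only".

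The protocol's Phase 3 reads differently. Section 2.0 says: "During Phase 3, we will recruit 200 individuals into a CET with two conditions". The Study Summary and section 12.0 give the same 200. Section 2.0 has the selected package "compared to individual HIV testing and counseling (IHTC) delivered as usual" and words the primary hypothesis "as compared with partnered YMSM who receive individual testing and counseling (only". Sections 2.0 and 6.0 let the index partner attend alone, with the partner, or alone first with the partner joining later. Under section 6.0 the index partner is randomised and a joining partner takes the same condition.

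Other protocol text does not fit this design. Section 24.0 still describes a coming RCT against standard CHTC. The inclusion criteria in section 10.0 still require both partners to agree to attend together.

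**The concern.** The SAP's only Phase 3 power statement differs from the protocol's Phase 3 in three respects: size, enrolment unit and comparator. Nothing in either document links the two designs. A null Phase 3 result would then be read against a power figure above .80 that was computed for another trial.

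Nor can a reader work out the right figure. The documents omit the number of arms simulated, the base rate of the outcome, the within-couple correlation, an effect size against IHTC, and whether partners who enrol later count toward the 200. The claim covers all direct effects, including the SAP's two couple-level outcomes. Those depend on what the primary partner reports or tests positive for, and the documents do not say how they are obtained when the partner is not enrolled.

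**Working it through.** **1. The designs side by side**

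| | SAP power analysis | Protocol Phase 3 |
|---|---|---|
| Size | 144 couples, 288 individuals | 200 individuals |
| Retained at 6 months | at least 232 | not stated |
| Arms | not stated | 2 |
| Enrolment | all in couples | solo, couple, or partner later |
| Comparator | CHTC alone; psychoeducation | IHTC as usual |

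**2. The plan's own figure.** 144 × 2 = 288, and implied retention is 232/288 = 80.6%. The > .80 itself cannot be reproduced: besides the omitted inputs already named, the growth-factor variances, allocation ratio and share not on PrEP are missing.

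A rough plausibility check compares two proportions (normal approximation, variance pooled under the null, two-sided .05, two equal arms, no clustering). The odds ratios are 1 − .56 = 0.44 and 1 − .83 = 0.17. The control risk is an assumption.

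| Assumed control risk | 20% | 30% | 40% | 50% |
|---|---|---|---|---|
| OR 0.44, 232 analysed | .58 | .73 | .82 | .86 |
| OR 0.44, 161 analysed | .43 | .57 | .66 | .71 |
| OR 0.17, 232 analysed | .97 | > .99 | > .99 | > .99 |
| OR 0.17, 161 analysed | .88 | .97 | > .99 | > .99 |

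So > .80 at 232 is attainable under some assumptions and not under others. This check ignores repeated measures and does not replace the simulation.

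**3. Size gap, from stated numbers.**

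- 200/288 = .694, so 31% fewer than simulated.
- 200/232 = .862, so 14% fewer than the SAP expects to retain.
- At the SAP's retention, 200 × .8056 = 161.
- 161.1/232 = .694, the same ratio as for enrolment.

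**4. Scaling one direct effect.** Power = Φ[(1.96 + z) × √r − 1.96], where z is the normal quantile of the starting power and r is the ratio of sample sizes (per-arm sizes if the number of arms changes). The test is two-sided at .05. Effect size and couple structure are held fixed.

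For example, with starting power .80 and r = .694: (1.96 + 0.842) × .833 − 1.96 = 0.375, and Φ(0.375) = .646.

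| Scenario | r | from .80 | from .85 | from .90 |
|---|---|---|---|---|
| Same arms, 200 counts both partners | 200/288 = .694 | .646 | .704 | .771 |
| Three equal arms of 96 simulated, two of 100 planned | 100/96 = 1.042 | .816 | .864 | .911 |
| 200 counts index partners only, all partners enrol, same arms | 400/288 = 1.389 | .910 | .942 | .969 |

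In the first scenario, .80 is kept only if the starting power was at least Φ(2.802/.833 − 1.96) = .920.

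**5. Solo enrolment.** For pairs, effective size is N/(1 + ICC). At an assumed ICC of .44, 288/1.44 = 200, so 200 unpaired participants would carry as much information on an individual-level outcome as 288 in couples. At a lower ICC they carry less, at a higher one more.

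**The case against.** The strongest reply is that the planned trial may be adequately powered. The SAP claims more than .80, so .80 is a lower bound on the starting figure. Protocol 5.0 says each of the three components has established efficacy. On that premise, a package of all three against IHTC could show at least as large an effect as ACT plus CHTC against CHTC alone. With the larger MI odds ratio, 161 retained participants give .88 or more at an assumed control risk of 20% or higher. Solo enrolment also removes within-couple correlation.

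All of that stands as possibility, and it is why the conclusion stops short of calling the trial underpowered. It does not supply support. Neither document gives an effect against IHTC, protocol 3.0 says CHTC has not been examined in young samples, and the 83% figure is given as an upper value against a different control. Solo enrolment helps only individual-level outcomes.

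Three further points are fair:

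- The SAP's numbers agree with one another, so this is a conflict between documents and not a miscalculation.
- Protocol 24.0 reads as leftover Phase 2 status text. The substantive comparator conflict is SAP 1.2 against protocol 2.0.
- The protocol equates 36 couples with 72 individuals for Phase 2, which suggests that its 200 individuals counts both partners. That makes the 400-person scenario less likely, but the counting rule for later-joining partners is still unstated.

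**Conclusion.** The concern holds. The > .80 statement belongs to a design of 288 individuals in couples, with effect sizes from contrasts other than IHTC. It is unsupported for a two-arm trial of 200 individuals against IHTC with optional solo enrolment. The size gaps (31% and 14%) follow directly from stated figures.

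The effect on power is undetermined. The illustrations run from about .65 to about .91 for a starting power of exactly .80, depending on points the documents leave open. They assume an unchanged effect size and unchanged retention, and they do not cover indirect effects or the couple-level outcomes. This must be fixed because the primary contrast and its sample-size justification disagree between the two governing documents.

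**What to change.** 1. Reconcile the Phase 3 size and comparator between SAP 1.2 and its Power Analysis section and protocol 2.0, 12.0 and 24.0. This includes the SAP hypothesis that still names CHTC only. Add the joint-attendance criterion in protocol 10.0 to the text to be reconciled.
2. State whether the 200 counts both partners, including those who join later.
3. Replace the 144 / 288 / 232 sentence with a Monte Carlo rerun for the reconciled design: two arms, and 200 individuals if that number is confirmed. State the solo/couple mix, retention, base rate, within-couple correlation, share not on PrEP, and a justified effect size against IHTC, with a range where an input is uncertain.
4. Report power or the minimum detectable effect separately for individual-level, couple-level and indirect effects. Remove > .80 unless the rerun supports it.

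The cost is one simulation rerun with newly stated assumptions and wording changes in both documents. If 200 is confirmed, no extra participants are needed. The downside is that the stated power may become less favourable.

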Baseline Visit – PHASE 2 (up to \$50)

1. Informed Consent process
2. STI testing (\$20)
3. CASI survey (\$10)
4. Randomization to one of three conditions (phase 2)
5. Session 1 (phase 2): will occur at this time in accordance with the randomized condition.
 - a. Condition 1: CHTC
 - b. Condition 2: ACT videos + CHTC
 - c. Condition 3: MI-CST + ACT videos + CHTC

FOR COUPLES WHO ARE ASSIGNED TO A CONDITION THAT INCLUDES VIDEOS, PARTICIPATING COUPLES WILL WATCH THE VIDEOS SEPARATELY. AFTER VIEWING THE VIDEOS SEPARATELY, A VIDEO RECOGNITION SURVEY (ATTACHED) IS COMPLETED BY THE COUPLE TOGETHER.

Baseline Visit – PHASE 3 (up to \$50)

1. Informed Consent process
2. CASI survey (\$30)

PROTOCOL TITLE:

3. Randomization
4. HIV testing (\$10)
5. STI testing (\$10)
6. Session 1: will occur at this time in accordance with the randomized condition.
 - a. Condition 1: individual HIV testing (IHTC) as usual condition
 - b. Condition 2: We Test intervention

Randomization Stratification: Randomization will be stratified by Site, Age (either partner under 18 vs both 18 & older), Race/Ethnicity (Both White vs not both White) and whether the index partner attended individual vs couple.

After completing the baseline assessment for both Phases 2 and 3, YMSM will complete follow-up assessments a month after baseline, and 3 months after baseline. In Phase 3, participants will also complete assessments at 6-months post-baseline. Online CASIs will be completed at each follow-up either at home or in-office. In addition, STI and HIV testing will occur at the 3-month and 6-month follow-ups. All follow-ups will be conducted individually to facilitate retention, even if the couples dissolve.

Immediate Post-Test Assessment (1 month after BL)

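### The claim of power above .80 for all direct effects has no basis for the two STI outcomes and does not describe Phase 3 as planned; the STI outcomes also need a stated two-wave model

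*SAP*

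**What the plan says.** SAP 1.2 names four primary indicators of transmission risk behavior. The second is the participant's own chlamydia or gonorrhoea diagnosis. The fourth depends on such a diagnosis in the primary partner. The first and third concern CAS with casual partners.

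SAP 1.2.1 puts every primary outcome into one multilevel latent growth model of the follow-up data. It has an individual-level intercept and linear slope, a quadratic if fit suggests it, and both growth factors regressed on condition. It does not say which variances are free at which level.

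SAP 1.2.2 (Power Analysis) describes a simulation in which "each individual provides data at 3 follow-up points". Its outcome effects are a "56% decrease in the odds of CAS with a casual partner" relative to CHTC alone and "as much as an 83% reduction in the odds of CAS with a casual partner" relative to a psychoeducation control. The remaining inputs are communication scores for the mediation path, and these too are linked to CAS. With 288 individuals and at least 232 retained, it claims power above .80 "for all hypothesized direct effects as well as indirect pathways".

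Protocol 6.0 states: "In addition, STI and HIV testing will occur at the 3-month and 6-month follow-ups". The visit headed "Immediate Post-Test Assessment (1 month after BL)" lists the CASI alone. The Phase 3 baseline visit includes an STI test, listed after randomization and before session 1. Protocol 2.0 gives the trial's size as "Phase 3 (n=200 individuals): involves a CET comparing the most promising intervention package", with individual HIV testing and counseling (IHTC) as the comparator.

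**The concern.** A reader will take the figure of .80 to cover all four primary outcomes. For two of them, the number of waves, the effect and the event rate were never STI inputs. The sample size and comparators behind the figure are also not those of Phase 3, so the CAS outcomes are affected too.

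The model form raises a second question. Two binary follow-up results per person are little to support an individual intercept, an individual slope and their covariance, and they cannot support a quadratic. If the SAP leaves this open, the analyst must decide after seeing the data whether to fix the slope variance or bring in the baseline test as a wave. That decision changes the meaning of the arm coefficient on the intercept. With follow-up waves only, it is a post-intervention difference. With baseline as the first wave, it is a difference before session 1, and only the slope coefficient is a treatment effect.

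**Working it through.** **1. The plan's own figure.** It cannot be reproduced: control rates, correlations, growth-factor variances, allocation and the share not on PrEP are not given. As a plausibility check, take one wave, 116 per arm (232/2, assuming 1:1), two-sided 5% and no clustering. At OR 0.44 (1 − 0.56), power is 0.58 at a 20% control rate and 0.82 at 40%. At OR 0.17 (1 − 0.83), it is 0.75 at 10% and 0.90 at 15%. So a figure above .80 is attainable, but only for suitable rates and effects.

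**2. Inputs for an illustration.** n = 232 (SAP), or 200 × 232/288 = 161 (the protocol's 200 at the SAP's retention). The ORs of 0.44 and 0.17 are CAS effects, borrowed here. Within-person and within-couple correlations (rw, rc) are assumed to be (0, 0), (0.2, 0.1) or (0.5, 0.2). For a common arm effect over k visits:

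Var(log OR) = [1/(p0q0) + 1/(p1q1)] × [1 + (k−1)rw + k·rc]/k ÷ (n/2)

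**3. Cost of two waves instead of three, equal positivity at each visit.** Only the middle factor changes.

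| rw, rc | k = 3 | k = 2 | Variance ratio | 80% power becomes |
|---|---|---|---|---|
| 0, 0 | 0.333 | 0.500 | 1.50 | 63% |
| 0.2, 0.1 | 0.567 | 0.700 | 1.24 | 71% |
| 0.5, 0.2 | 0.867 | 0.950 | 1.10 | 76% |

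**4. The same cost if infections accrue.** Suppose a constant monthly risk h, with each infection found at the next test. The control rate at a visit is then 1 − (1−h)^(months since the last test). Apply OR 0.44 at each visit, n = 232, no correlation, and sum the information over visits. Months 3, 6 against months 1, 3, 6 give:

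| h per month | Variance ratio | Power, three tests to two |
|---|---|---|
| 1% | 1.005 | 22.1% to 22.0% |
| 3% | 1.016 | 53.0% to 52.4% |
| 6% | 1.034 | 80.5% to 79.2% |

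**5. Control positivity per visit needed for 80% power on two waves (equal positivity).**

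| rw, rc | n=232, OR 0.44 | n=161, OR 0.44 | n=232, OR 0.17 | n=161, OR 0.17 |
|---|---|---|---|---|
| 0, 0 | 17% | 26% | 7% | 10% |
| 0.2, 0.1 | 25% | 40% | 10% | 14% |
| 0.5, 0.2 | 37% | unattainable (maximum power 74%) | 13% | 19% |

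Worked example for the first cell: p0 = 0.173 gives p1 = 0.084. The bracket is 6.99 + 12.96 = 19.95. Multiplied by 0.5 and divided by 116, this is 0.086, so SE = 0.293. Then 0.821/0.293 − 1.96 = 0.84, which is 80% power.

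**6. Identification on months 3 and 6.** For people enrolled alone, two binary results give 3 free pattern probabilities per arm, 6 in all. The model has 7 parameters: two means, two arm effects, two variances and a covariance. The rank is 6, so it is not identified. With slope variance fixed at zero it is identified (5 of 5), and so it is with free slopes and baseline added as a wave (7 of 7).

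For complete couples, the rank and singular values of the scaled Jacobian were computed at illustrative parameter values. A couple-level intercept and slope plus a person intercept is identified (8 of 8, smallest singular value 0.128). Adding the person slope variance and covariance (10 parameters) drops the smallest value to 0.002; adding baseline as a wave restores it to 0.076. The model proposed under the fix has 5 parameters and a smallest value of 0.278.

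**The case against.** Three points on the other side have force.

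First, a reader might infer that STI power falls short of .80. The documents do not support this. They give no STI rate, effect or correlation, and the illustrations borrow CAS odds ratios. At OR 0.17 the required positivity is modest.

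Second, a reader might infer that losing the month-1 test is itself costly. That holds only if each visit has equal positivity, so that omitting one removes a third of the events. Tests at months 3 and 6 cover the same six months as tests at 1, 3 and 6. If infections accrue and persist to the next test, the loss is 0.5% to 3%. Neither assumption is in the documents, so both must be shown.

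Third, a reader might infer that the growth model cannot be fitted to the STI outcomes at all. SAP 1.2.1 fits one pooled model with individuals nested in couples, and a version in which only the couple-level slope varies is identified. A baseline STI test exists, and adding it as a wave also identifies the model. What stands is narrower. The SAP speaks of follow-up data and leaves the variance structure unstated, Phase 3 lets people enroll alone, and the form with a free individual slope is unidentified for them and at best weakly identified in couples.

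None of this rescues the power statement. It makes no exception by outcome, and its three follow-up points are true of the survey but not of the STI tests.

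**Conclusion.** The power claim is wrong as written. For outcomes 2 and 4 it is unsupported: two follow-up tests rather than three, and no STI rate or effect. For the CAS outcomes it describes 288 individuals and the source studies' comparators, not 200 individuals against IHTC. This much rests on the documents alone.

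The size of any shortfall cannot be fixed from the documents. Under the stated illustrations, the two-wave variance penalty runs from about 1.005 to 1.50. The control positivity needed at OR 0.44 runs from 17% to 37% with 232 retained, and from 26% to unattainable with 161. These figures assume that CAS odds ratios carry over to STIs, 1:1 allocation, the SAP's retention and the correlations listed; the positivity figures also assume equal positivity at each visit.

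The model form is a gap that is cheap to close, not a proof that the analysis must fail. Only the quadratic is ruled out outright on two waves. Which participants can contribute to the couple-level outcomes is a separate question, not settled here.

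**What to change.** **(a) SAP 1.2.2 (Power Analysis).** Withdraw the figure of .80 for outcomes 2 and 4. For the CAS outcomes, either label it as applying to 288 individuals and to the comparators of the source studies, or re-simulate at the planned 200 against IHTC. If STI power is to be claimed, simulate tests at months 3 and 6 with a stated STI rate, effect and correlation, and show the range.

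**(b) SAP 1.2.1.** For outcomes 2 and 4, replace the individual random slope and quadratic with a two-wave model of the month 3 and 6 results. Include a visit term and one post-baseline arm coefficient as the treatment effect. Use either logistic regression with person and couple random intercepts, or couple-clustered GEE. Choose one in advance, because the first gives a conditional odds ratio and the second a population-averaged one; do not switch on non-convergence.

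Adjust for the participant's own baseline STI result only if the sample preceded any session 1 in that couple. In Phase 3, "Session 1: will occur at this time in accordance with the randomized condition", and a partner may join after the index partner has attended alone. Do not adjust for a partner's result taken after the index partner's session 1. State how a missing baseline result is handled.

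**(c) Mediation, SAP 1.2.1.** Drop the STI outcomes from the growth-factor analysis, or restate it for them without an outcome slope.

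**Cost.** Wording only if the claim is withdrawn and labelled; new simulations otherwise. No new visits or data. The price is a narrower power statement and no individual STI trajectory.
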